The study will be conducted according to Good Clinical Practice (GCP) guidelines, the U.S. Code of Federal Regulations (CFR) Title 21 CFR (Part 50 – Protection of Human Subjects and Part 56 – Institutional Review Boards) and the Declaration of Helsinki. This protocol will be submitted to the IRB at the Western IRB for approval and will be reliably reviewed at UAB. The informed consent of each subject will be obtained in accordance with 21 CFR Part 50 and the Declaration of Helsinki before protocol-specified procedures are carried out.

A study research assistant will obtain the participant's written informed consent prior to any study-related procedures. Consent will be documented by the dated signature of the subject. The signature confirms that the consent is based on information that has been understood. Each subject's signed informed consent form will be kept in secure files by the investigators for possible inspection by regulatory authorities.

Potential Benefits of Proposed Research to the Participant and Others

The potential benefits to an individual participant in the study are not known. The potential benefits of the study to others could be considerable. If our hypotheses are true, this study will make a significant contribution towards helping PLWH who are virally unsuppressed improve adherence to their antiretroviral therapy (ART) regimen and ultimately achieve viral suppression. If the intervention is effective, the direct benefit to participants is the increased ART adherence, retention in HIV primary care, and viral suppression. Increasing ART adherence for PLWH will yield significant benefits in current efforts to achieve HIV elimination. Possible risks (i.e., discomfort answering questions, potential confidentiality breaches) are outweighed by the new knowledge gained regarding increasing ART adherence among PLWH.

Importance of Knowledge to be Gained

The knowledge gained from this research will enable the scientific community, clinicians, and PLWH to improve the HIV care continuum in the US. Consistent with the priorities of RFA-NR-20-002, findings from this study will focus on the efficacy of an adaptive Community Health Worker intervention to improve HIV care among PLWH.

Data and Safety Monitoring Plan

Data and Safety Monitoring Plan is attached separately.

ClinicalTrials.gov Requirements

This trial will be registered with ClinicalTrials.gov.

References

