Community Health Worker And MHealth to ImProve Viral Suppression
(CHAMPS)

NCT04562649
05/23/2023

STUDY PURPOSE AND RATIONALE

Persons living with HIV (PLWH) now achieve a near-normal life expectancy due to antiretroviral therapy (ART) which has transformed HIV from a terminal diagnosis to a manageable chronic condition.¹⁻⁴ Despite widespread availability of ART in the United States (US), many of the country's approximate 1.1 million PLWH⁵—in diverse geographic locations—are not fully benefitting from ART due to poor adherence.⁶ Suboptimal ART adherence is a challenge in the US South which accounts for 51% of new domestic cases annually.⁷ The Southern HIV epidemic is even more pronounced in the “Deep South”⁸ with striking numbers in Alabama (AL) where PLWH experience poor viral suppression (62%).⁹ Likewise, the heavy HIV burden in the US Northeast¹⁰ is in New York City (NYC) which accounts for 82% of all PLWH in NY state.¹¹ Further, in the NYC region, only 67% of PLWH achieve sustained, or durable, viral suppression (the ultimate goal of ART). In response, the US government prioritized four NYC-area counties and AL (our study sites) as five of 55 areas with a substantial burden of HIV in the Ending the HIV Epidemic (EHE) plan.¹² These suboptimal HIV health outcomes occur at a time when clinicians have limited time and the US healthcare system remains fragmented,¹³ further exacerbating the challenges inherent in the lives of underserved, marginalized groups, such as PLWH.¹⁴ Therefore, the development and evaluation of interventions using a cadre of community health workers (CHW) holds promise for addressing these challenges in the US.^{15, 16} Yet, research is urgently needed to bring CHW interventions to scale, particularly in EHE priority locations.

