We have estimated the statistical power for the primary outcome of viral suppression (viral load ≤ 200). We will recruit and enroll 300 participants (n=150 in each site) and use a 1:1 random assignment to the intervention arm and the control arm (i.e., 75 in each arm per site). We estimate the statistical power to examine efficacy of the intervention at six months for the total subjects. All power estimations are based on $\alpha=0.05$ and 2-sided tests and following assumptions: (1) an 80% retention rate, at each follow-up assessment for each study arm (based on our 86.1% retention rate in New York City WiseApp trial); (2) a correlation of 0.6 of outcome measure for participants at different time points of assessment; (3) an intra-cluster correlation (ICC) of 0.2 of participants of same study sites; and (4) 75% baseline viral suppression rate (based on preliminary data of the BA2C study).

For the total sample (n=300), the proposed study will have at least 80% power to detect a difference of 12% or greater in viral suppression. The 12% difference in viral suppression is equivalent to a small effect size (Cohen's D of 0.31). Therefore, the proposed study will have sufficient power ($\geq 80\%$) to detect a small effect size or greater. Based on findings from our BA2C and WiseApp interventions, we expect a combined improvement of 12% on viral suppression as compared to the control arm.

We have also estimated the statistical power to assess sustainability of the intervention at 12 months. For this analysis, we will conduct a non-inferiority test of viral suppression at Month 12 as compared to Month 6. This study will have at least 80% power to conduct a non-inferiority test with a margin of 10%.

Sampling approach to successfully enroll PLWH who are not optimally engaged in HIV Care: Using active and passive recruitment methods, the project coordinator at each site will oversee and participate in recruitment efforts. The study staff hired through this project and the peer-to-peer networking efforts at each site will be used to recruit study participants. Our study team at both sites has extensive experience in recruitment efforts for projects similar to the one proposed here and will be able to successfully recruit the study sample.

Eligibility Screening

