The distribution of all variables will be assessed, as will the correlations between all variables and the primary/secondary outcomes. We will assess for patterns of missing data, which are expected to be low as the study utilizes computer-assisted self-interview (CASI) for sensitive data, which reduces participant nonresponse. The primary anticipated reason for missing data is attrition due to loss to follow-up. Based on our preliminary studies, we are accounting for 20% attrition from randomization to the 12-month assessment.

All multivariate analyses will be preceded by standard descriptive bivariate analyses to describe key variables and relationships among them. These analyses will include means, frequency tables, histograms, and examination of distributions. All statistical tests will be two-sided tests with the level of significance at 0.05. The primary hypothesis 1 will be a comparison of viral suppression (primary outcome) between CHAMPS and standard of care. We will also compare the drop in viral load (measured in logarithmic scale with base 10) between the two groups. Our secondary and related outcome is ART adherence measured in two ways: 1) a single-item self-report measure, an empirically validated instrument (SRSI)¹⁰¹ and 2) electronic pill bottle data which we will be collecting in the intervention group since all participants will receive a CleverCap bottle for their medications. All the analyses will be based on initial assignment to groups, using the intention-to-treat principle.^{131, 132}

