The primary hypothesis 1 (H_1) will be tested using a generalized linear mixed model (GLMM) with logit-link function for binary outcomes (i.e., viral suppression) or a linear mixed model (LMM) for continuous outcomes (i.e., viral load measured in logarithmic scale) to account for the non-independence of repeated measurements within individuals.¹³³ The models will include a random intercept and fixed effects for intervention group, time, and interaction term of group and time which is for testing efficacy of the intervention. The model may include stratification variables, such as study site, age, and sex as covariates. A site by group interaction will be also examined and included in each model (above) if significant at the .05 level. All analyses will be tested for goodness-of-fit using the Wald-type test, which shows satisfactory performance for models with fewer (<5) covariates.¹³⁴ A similar GLMM will be used to test sustainability of the intervention at month 12. For this analysis, we will conduct a non-inferiority test¹³⁵ to compare viral suppression rate between month 12 and month 6. For primary hypothesis 2 (H_2), testing for intervention effect on ART adherence measured by SRSI (secondary outcome), we will use a similar LMM as mentioned above. For electronic pill bottle data in the intervention group, we will also examine the trend of electronic pill bottom data over time with a GLMM which will include a first-order autoregressive (AR1) covariance structure, as described by Hedeker and Gibbons.¹³³ We will also aggregate the electronic pill bottle data at different time points (0, 6, and 12 months) and examine the association between the electronic pill bottle data and ART adherence data measured by SRSI using Spearman nonparametric correlation.¹⁰¹ Similar GLMMs or LMMs will be used for secondary outcomes, with GLMMs for binary outcomes and LMMs for continuous outcomes.

Aim 2: Identify mediators and moderators of CHAMPS on study outcomes.

Data Analysis

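### The stated 80% power floor lists a site ICC of 0.2 with no source or role, and the planned month-6 test has about 77-78% power

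*Combined protocol and SAP*

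**What the plan says.** All references are to the combined protocol and SAP.

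- **Sample Size and Power Calculation.** 300 participants are randomized 1:1, "i.e., 75 in each arm per site". The assumptions are 80% retention at each follow-up, a correlation of 0.6 between time points, "an intra-cluster correlation (ICC) of 0.2 of participants of same study sites", and 75% suppression at baseline. The result is "at least 80% power to detect a difference of 12% or greater in viral suppression" at six months, with an equivalent Cohen's D of 0.31. The 80% level is given twice, both times as a minimum. No formula or software is named. The same section cites 86.1% retention in the WiseApp trial.
- **Aim 1, Data Analysis.** "All statistical tests will be two-sided tests with the level of significance at 0.05". The primary model is a logit mixed model with a random intercept and "fixed effects for intervention group, time, and interaction term of group and time which is for testing efficacy". Site is called a stratification variable that may enter as a covariate. There is no random effect for site.
- **Study Outcomes.** Suppression at 6 months is the primary outcome. Viral load is also measured at 12 months, so the interaction has more than one term, and the analysis section does not say which one is the primary test.

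**The concern.** A power statement should follow from its listed assumptions and the planned test. Here one assumption has no visible function. A site ICC matters when sites are the unit of randomization, or when the model carries a site variance; neither applies. A reader cannot tell whether 0.2 raised the power, lowered it or was left out.

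It therefore has to be asked whether the planned test reaches 80% without it. If it does not, a null result would be read as coming from a slightly better-powered trial than was run, and the text would state a minimum that its own model does not meet.

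**Working it through.** **Inputs.** Control 75%, intervention 87% (75 + 12), 150 per arm at baseline, 120 per arm at month 6 (150 × 0.80), correlation 0.6, two-sided 0.05. All are from the power section. The binomial variances are 0.75 × 0.25 = 0.1875 and 0.87 × 0.13 = 0.1131.

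**Plan's effect size.** 0.12 / √[(0.1875 + 0.1131)/2] = 0.12 / 0.388 = 0.31. This reproduces.

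**Does the ICC enter?** The group-by-time contrast compares within-person changes, and a participant's site is the same at both visits. If the total correlation of 0.6 includes 0.2 from site, the within-site correlation is 0.4/0.8 = 0.5. The change-score variance factor is then 0.8 × 2(1 − 0.5) = 0.8, the same as 2(1 − 0.6) = 0.8 with no ICC. The site effect cancels.

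**Plan's power, closed-form approximations without the ICC.**

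1. Change score on 120 completers per arm: variance factor 0.8, power 76-77%.
2. Linear group-by-time contrast using all baselines: variance 2[(1 − 0.6²)/120 + (1 − 0.6)²/150] = 2(0.005333 + 0.001067) = 0.0128; 0.31/√0.0128 = 2.740; Φ(2.740 − 1.96) = 78.2%.
3. The same contrast on the log-odds scale: the effect is ln(0.87/0.13) − ln(0.75/0.25) = 0.802. The variances of the change are 0.0341 (control) and 0.0490 (intervention). 0.802/√0.0831 = 2.783, power 79.5%.
4. Risk-difference scale with exact binary variances, 120 completers: control 2 × 0.1875 × 0.4 = 0.150; intervention 0.1875 + 0.1131 − 1.2√(0.1875 × 0.1131) = 0.126; 0.12/√(0.276/120) = 2.50, power about 71%.
5. Common baseline, linear: 2(1 − 0.36)/120 = 0.01067; 0.31/√0.01067 = 3.002, power 85.1%.

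**The planned model, simulated.** The logit random-intercept model was fitted to simulated trials with 87% at both intervention follow-ups (an assumption, because the plan gives no month-12 rate), correlation 0.6 at 75%, and no site term. The Monte Carlo standard error is about 1 point.

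| Test at month 6 | Power |
|---|---|
| Group-by-month-6 term, three visits | 77.7% and 78.1% (1,500 trials; same participants missing both follow-ups, or independent missingness); 77.4% (1,600 trials); about 77% (2,000 trials) |
| Same, baseline and month 6 only | 75.2% to 75.5% |
| Common baseline, three visits | 83.6% to 84.0% |
| Common baseline, two visits | about 81% |

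**Retention at 86.1%.** This gives 150 × 0.861 ≈ 129 per arm. Line 2 becomes 2(0.64/129.15 + 0.16/150) = 0.01204; 0.31/√0.01204 = 2.825, power 80.6%. Line 3 becomes 82.0%. Line 2 gains 80.6 − 78.2 = 2.4 points. Adding that to the simulated 77-78% gives about 79-80%; adding it to 75.5% gives about 78% for the two-visit version.

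**Difference detectable with 80% power.** Using the change-score approximation, solve d = (1.96 + 0.842)√[0.8(0.1875 + p(1 − p))/120] with p = 0.75 + d. At d = 0.1247 the right side is 2.802 × 0.0445 = 0.1247, so about 12.5 points.

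**The case against.** The strongest reply is that this is rounding. The closed-form results run from about 71% to 85% according to method, and 78.2% and 79.5% sit close to 80%. A log-odds contrast on completers gives about 81%, and a baseline-adjusted analysis 85%. For the single run at 78.1%, the 95% Monte Carlo interval (76.0-80.2%) includes 80%. The plan also assumes 80% retention while citing 86.1%. The analysis is loosely specified too: covariates are optional, so no single power figure belongs to it.

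Much of this stands. The gap is small, and better retention would about close it. What does not stand is the defence of a minimum. The separate simulations of the random-intercept model all fall at 77-78%. The 81% figure is a completers-only contrast rather than a fit of that model, and the 85% belongs to a baseline-adjusted test that the plan does not specify.

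Stronger readings are tempting, but the documents do not support them:

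- *The protocol's own rates rule out an ICC of 0.2.* The background gives 62% suppression for Alabama and says "only 67% of PLWH achieve sustained, or durable, viral suppression" in the NYC region. Taken at face value these imply an ICC of about 0.003 (0.05²/4 ÷ 0.229) to 0.005 (0.05²/2 ÷ 0.229). But they are area figures with different definitions, not rates in trial participants. Two sites cannot exclude an ICC: with 0.2, a gap of 5 points or less still has a 13-15% chance. The value looks large; it is not refuted.
- *A 12-point gain would pass 100% at the better site.* One SD either side of 75% is 75 ± 19.4, about 56% and 94%. On the planned logit scale the effect is an odds ratio of 6.69/3 = 2.23, which moves 55.6% to 73.6% and 94.4% to 97.4%.
- *Only about 10 effective participants remain.* That applies a cluster design effect (240/24.8) to an individually randomized trial. Nothing suggests that the sponsor did so.
- *True power is 66-67%.* That is a month-6 comparison ignoring baseline, which is not the planned test.
- *The 80% was obtained through the ICC.* Treating 0.2 as variance removed by site, with 0.6 left intact, gives a factor of 0.8 × 0.8 = 0.64 and 85%. No passage says this was done.

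**Conclusion.** The point holds in a limited form. The ICC of 0.2 is unsourced, its use is unstated, and it has no place in an individually randomized comparison balanced within site. Under the stated assumptions the planned month-6 group-by-time test has about 77-78% power, 2 to 3 points below the stated minimum, or about 75% if month 12 is not modelled. This is a defect in a stated figure, not evidence of a seriously underpowered trial.

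The result rests on 75% control suppression, exchangeable correlation of 0.6 at that rate, 87% at both intervention follow-ups, and balance of arms within site. That balance comes from the power section and from site being called a stratification variable; the Randomization section does not itself name strata. The 75% rate drives power more than anything discussed here, and it sits uneasily with a population described as virally unsuppressed. That is a separate question.

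**What to change.** 1. Delete the ICC of 0.2 from the assumptions. If it is kept, give its source and say exactly how it enters the calculation.
2. Include site as a fixed covariate in the primary model instead of leaving it optional.
3. Define the primary test as the single arm contrast at month 6, in the same logit mixed model, with both arms sharing one baseline parameter (no group term at baseline). Randomization justifies this constraint. Power is then about 84% with three visits, or 81% with two, and the stated minimum becomes true.
4. State the method used to compute power.
5. If the model stays as written, restate power as about 77-78% for 12 points, or 80% for about 12.5 points (change-score approximation).

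A common baseline is one legitimate choice, not the only one. Whichever is taken should be fixed and dated before outcomes by arm are examined.

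The cost is a revised power paragraph and one model constraint, with no extra participants. The only downside is that, if the model is not changed, the published power becomes slightly less favourable.

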(WiseApp). Guided by a rigorous theoretical model of supportive accountability, the literature and our preliminary work support the scientific premise that adding WiseApp to the CHW intervention will enable PLWH to self-manage their ART regimens while CHW monitor their ART adherence in real-time ultimately leading to viral suppression and ART adherence. The proposed study will provide further information regarding the successful wide-scale implementation of this combination intervention in two high priority settings.

The proposed study will test the clinical efficacy and assess the implementation factors of the resultant CHW intervention, **Community Health Worker And MHealth to ImProve Viral Suppression (CHAMPS)**, through the following specific aims with virally unsuppressed adult PLWH (n=150 in AL and 150 in NYC):

1: Conduct an RCT to assess the efficacy and sustainability of CHAMPS on viral suppression (primary outcome) and ART adherence (secondary outcome) compared to the standard of care (standard of care, control group) over 6 and 12 months.

PLWH randomized to CHAMPS will have significantly greater:

H₁: Viral suppression (primary outcome) than those in the standard of care group.

H₂: ART adherence (secondary outcome) than those in the standard of care group.

2: Identify mediators and moderators of CHAMPS on study outcomes.

H₃: HIV medication taking self-efficacy, motivation expectancies, self-regulation skills, and HIV-related stigma mediate the effect of CHAMPS on viral suppression and ART adherence.

H₄: Depression, anxiety, and substance use moderate the strength of the effect of CHAMPS on viral suppression and ART adherence.

3: Guided by the Reach Effectiveness Adoption Implementation Maintenance (RE-AIM) framework, identify multi-level factors associated with successful implementation of CHAMPS to inform future implementation and scale-up.

This study seeks to expand and strengthen a CHW model through an extant mHealth approach. Findings will inform the effect of CHAMPS on outcomes related to the HIV Care Continuum in two EHE priority settings.

Theoretical Framework

The intervention is guided by the conceptual model of supportive accountability illustrated in **Figure 1**.⁸⁶ The model is based on the premise that human support increases medication adherence through accountability to a coach (in CHAMPS – a CHW) who is perceived as trustworthy, knowledgeable, and benevolent.

[figure not shown]

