2) **WiseApp** is derived from formative work funded by and in collaboration with the CDC (U01PS003715) to design a self-management app for PLWH⁸⁴ with the goal of being more widely applicable across chronic illness populations who require medications and adding self-management strategies. A comprehensive process for the design of the self-management app was guided by the Information Systems Research (ISR) framework and incorporated end-user feedback throughout the design process.⁸⁵ The resultant WiseApp is comprised of the following functional components: 1) testimonial videos of PLWH, 2) push-notification reminders, 3) medication trackers, (4) health surveys, and (5) a “To-Do” list outlining their tasks for the day, such as medications to take (See Figure 2). A key component of WiseApp is a medication tracker linked to an electronic pill bottle and a capability to link to a fitness tracker and monitor physical activity. WiseApp can then send tailored reminders based on the feedback from the linked devices, such as medication reminders if the pill bottle has not been opened. Additional images of the WiseApp are found in Table 2. The WiseApp is aligned with the NINR Strategic Plan⁷⁶ and is currently being evaluated in an RCT (NCT03205982) in 200 PLWH with poor ART adherence in NYC (R01HS025071, PI: [name]). Preliminary data show evidence for the success of this intervention in comparison to the control group for improving ART adherence (primary outcome) (58% ART adherence, 47% ART adherence, respectively, p=0.03) in low-income racial and ethnic minority PLWH (mean age=49.1 years, SD±10.6).

STUDY DESIGN

Aim 1: Assess the efficacy and sustainability of CHAMPS on viral suppression (primary outcome) and ART adherence (secondary outcome) compared to the standard of care (standard of care, control group) over 6 and 12 months.

Design Overview

A randomized controlled trial will be conducted with 300 PLWH (n=150 in AL and 150 in NYC) over 12 months. Participants will be randomly assigned to CHAMPS (intervention) or a standard-of-care control arm.

Intervention Arm. The CHAMPS intervention, outlined in Table 1, is a 6-month intervention guided by BA2C.¹⁷ The CHW will be demographically-matched to our study participants.

Intervention Training and Support. The CHW will be trained on the intervention: content of each session, MI, strengths-based case management, ARTAS,¹⁷ HIV and substance

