Upon arrival at the screening visit, we will collect written informed consent prior to enrolling into the study trial (See Protection of Human Subjects). The informed consent form provides details of the study procedures, risks, benefits, site contact information, and the nature of confidentiality and voluntary participation. The consent process also covers information on the trial and compensation for time.

Participants in both the intervention and control arms will visit the study sites (BAO/1917 Clinic-AL and Columbia University School of Nursing-NYC) at the screening, baseline, 6, and 12-month visits. Following the completion of the baseline study instruments, study participants in the CHAMPS intervention arm will be given a CleverCap™ Lite dispenser and trained on how to use it; they will also be trained by study team members on how to use the different features of the Wise App and receive medication reminders. Upon assignment to the intervention arm, a CHW is assigned to and meets with the participant as soon as possible, generally on the same day but no more than five business days. The CHW will deliver the interventions outline in Table 3 either in-person or remotely throughout the course of the study.

Participants will be texted appointment reminders for study visits. Hard to reach participants will also be sent scheduling reminders. These reminders will be sent via Qualtrics, REDCap and/or encrypted e-mails from the study's secure CUMC e-mail address.

Participants in both arms will receive \$40 at baseline, \$50 at 6-months, and \$60 at 12-months as a token of appreciation for their time participating in the study visits and for their blood draws. Participants who complete Qualitative Interviews will be compensated \$40 for completing that interview.

Overview of Data Collection Time Points

Follow-up visits will be scheduled 30 days before to 30 days after the target window based on participant availability and site capacity. Timing of follow-up visits is scheduled to allow site flexibility while still scheduling follow-up visits within a reasonable time span.

Sound Retention Efforts

Using the retention efforts described above and in the Recruitment and Retention attachment, we are confident that we will retain at least 80% of our study sample at the follow-up assessments as we have done previously.¹¹⁴

Data Management

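### Aim 1 sets sustainability against standard of care, but the only designated test compares month 12 with month 6: no month-12 between-arm contrast is named, and the result does not depend on H1.

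*Combined protocol and SAP*

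**What the plan says.** Aim 1, in the specific aims and again under Study Design, covers both efficacy and sustainability on viral suppression, "compared to the standard of care (standard of care, control group) over 6 and 12 months". Study Outcomes fixes the primary outcome at 6 months, and Sample Size and Power Calculation powers the efficacy comparison at six months only.

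The power section then turns to month 12: "We have also estimated the statistical power to assess sustainability of the intervention at 12 months". The method is that "we will conduct a non-inferiority test of viral suppression at Month 12 as compared to Month 6", and the study is said to have at least 80% power "to conduct a non-inferiority test with a margin of 10" percent. Data Analysis under Aim 1 repeats this: "A similar GLMM will be used to test sustainability of the intervention at month 12", with a non-inferiority test "to compare viral suppression rate between month 12 and month 6". Neither section names the arm, a control reference, the scale of the margin or its basis.

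Three other places bear on the point:

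- Procedures: "Participants in both the intervention and control arms will visit the study sites" at screening, baseline, 6 and 12 months, and Table 4 schedules viral load at month 12. The data for a between-arm comparison will therefore exist.
- Table 5 (RE-AIM) lists between-group comparisons under Efficacy and 12-month efficacy under Maintenance, but gives no test, time-specific contrast or success rule.
- The mediation analysis under Aim 2 is conditional on the intervention arm having improved more than control. The sustainability test carries no such condition.

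**The concern.** The aim is comparative; the test assigned to it is not. A month-12 versus month-6 comparison answers whether the suppression rate has fallen. That is a legitimate question, but a benefit over standard of care can be absent from the start, or can disappear because control improves, without any fall in the CHAMPS rate. Control improvement is not far-fetched here: the Preliminary Data section reports that both arms of BA2C improved, with no significant difference between them.

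Two separate gaps follow. Without dependence on H1, a flat rate can be reported as sustained when there was no effect to sustain. Without a month-12 between-arm contrast, it can be reported as sustained when the arms no longer differ. At stake are a named Aim 1 conclusion and the RE-AIM Maintenance item that relies on 12-month efficacy.

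**Working it through.** **Inputs** (Sample Size and Power Calculation unless noted): 150 per arm; 80% retention at each follow-up, so 0.80 × 150 = 120 per arm; within-person correlation 0.6; 75% baseline suppression; a 12-point difference, so 87% versus 75%; margin 10%; two-sided 0.05 (non-inferiority is judged on the lower limit of a two-sided 95% interval). My assumptions: the test is run in the CHAMPS arm, the margin is absolute, the same 120 people per arm have both visits, and the site intra-cluster correlation of 0.2 is not applied.

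**1. The plan's own figure.** For one arm,

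SE² = [p6(1−p6) + p12(1−p12) − 2·0.6·√(p6(1−p6)·p12(1−p12))]/120

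Pass probability = Φ((p12 − p6 + 0.10)/SE − 1.96)

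At 75% on both visits: SE² = (2 × 0.1875 × 0.4)/120 = 0.00125, so SE = 0.0354. Then Φ(2.83 − 1.96) = 80.7%, which reproduces the stated figure of at least 80%. At 87% on both visits the same formula gives 95%, and pooling both arms (240 people at 75%) gives 98%. The stated figure is therefore consistent with a single-arm test but does not by itself identify the arm.

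**2. What the test does detect.** True falls in CHAMPS from 87% pass with probability 54% (4 points), 26% (6 points) and 2.5% (10 points). It works as a test of decline.

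**3. What it does not detect.** I simulated 400,000 trials per scenario with 120 per arm, paired binary outcomes at correlation 0.6 and unadjusted Wald tests. H1 and the month-12 test count as successes only when they favour CHAMPS. Rates are month 6/month 12; NI is the plan's non-inferiority test and M12 the month-12 between-arm test.

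| CHAMPS | Control | NI | H1 and NI | H1 and M12 | All three |
|---|---|---|---|---|---|
| 75/75 | 75/75 | 81% | 1.6% | 0.7% | 0.6% |
| 87/87 | 75/75 | 94% | 62% | 54% | 52% |
| 87/87 | 75/81 | 94% | 62% | 23% | 23% |
| 87/87 | 75/87 | 94% | 62% | 2.7% | 2.7% |
| 87/86 | 75/86 | 88% | 57% | 2.6% | 2.6% |

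Row 1 shows what the H1 gate achieves. Rows 2 to 4 show what it does not: H1 plus non-inferiority stays at 62% whatever control does after month 6, because the non-inferiority test never uses the control arm. The documents give no month-12 rates, so rows 3 to 5 are illustrations.

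**4. Power of the missing contrast.** For 87% versus 75% at month 12, SE = √((0.1131 + 0.1875)/120) = 0.0500, so power is Φ(0.12/0.0500 − 1.96) = 67%. The probability that both visits are significant (bivariate normal, correlation 0.6) is 54%. Using the baseline value changes this:

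- Change from baseline with a common variance (factor 2(1 − 0.6) = 0.80): SE 0.0448, power 76%; correlation between visits 0.4/0.8 = 0.5, both visits 64%.
- Change from baseline with visit-specific binomial variances (75% baseline in both arms): SE 0.0479, power 71%; correlation between visits 0.564, both visits about 57%.
- Baseline adjustment (factor 1 − 0.36 = 0.64): SE 0.0400, power 85%; partial correlation (0.6 − 0.36)/0.64 = 0.375, both visits 75%.

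**The case against.** The strongest reply is that the comparison is already within reach. H1 is tested in a repeated-measures model with group, time and group-by-time terms, both arms are measured at month 12, and the sustainability model is described as similar. If time is categorical, that model yields a month-12 between-arm estimate. This is true, and it is why the remedy is cheap. But the interaction is assigned to efficacy with no month named, and the sustainability sentence then specifies a different contrast. The month-12 difference has no label, stated power or success rule.

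It is also fair to say that 81% is not an error rate. It is the test's power when nothing has changed, and a finding of no decline would be correct. The plan does not say it would claim sustainability after a failed H1, and speaking of an intervention's sustainability arguably presupposes an effect. What stands against this is that nothing in the plan rules the claim out, although the authors did condition the mediation analysis on benefit.

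Two smaller points are right. The simulated tests are unadjusted comparisons at each visit, not the planned mixed model, so the joint percentages are indicative. And the absolute scale of the margin can be inferred from the same section's use of 12% for an absolute difference; what is missing is an explicit statement, the arm and the basis for 10 points.

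**Conclusion.** The concern holds. Followed as written, the plan can return a sustainability result when no benefit over standard of care exists or remains. With no effect at all the designated test passes 81% of the time, against 1.6% if H1 must also succeed. Where CHAMPS holds at 87% and control catches up fully by month 12, H1 plus non-inferiority still succeeds 62% of the time, against 2.7% when a month-12 between-arm test is required with H1. The two gaps are distinct, and closing one does not close the other.

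These sizes rest on a single-arm reading of the test, 120 people per arm with both visits, and the hypothetical month-12 control rates. If 80% retention at each visit left only 0.80 × 120 = 96 with both, the non-inferiority power at 75% would be 72% rather than 80.7%. The argument itself does not depend on these values, since the test makes no use of control data. The month-6 primary analysis is not affected, and the stated non-inferiority power is not wrong. This should be fixed, but it does not undermine the trial.

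**What to change.** 1. Designate the month-12 CHAMPS minus standard-of-care difference in suppression, from the same longitudinal model and with a 95% confidence interval, and require it for any claim of sustained benefit over control.
2. Test that contrast, and interpret the non-inferiority result as sustainability, only if the month-6 H1 test is significant.
3. Keep the month-12 versus month-6 test as the measure of durability. Name the CHAMPS arm, and state the margin as absolute, with its basis.
4. State the power of the month-12 contrast and whether it uses the baseline value.

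The change is to analysis and power text only: no new participants, visits, data or model. The real cost is a harder claim. If the full 12-point effect persists, the month-12 contrast has about 67% power unadjusted, 71% to 76% as change from baseline, and at best about 85% with baseline adjustment at correlation 0.6. Success on both H1 and the month-12 contrast is about 54% unadjusted and about 75% adjusted. Requiring non-inferiority as well gives about 52% unadjusted, against 62% for H1 plus non-inferiority alone.
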